#### **6.3.4.3. Telephone Follow-up**

Subject is contacted the following morning, by RC and/or PI. The purpose of the phone call will be to enquire about the subject's wellbeing since leaving the PET Centre.

#### **6.3.5. Unscheduled Visits**

Subjects may need to return to the site for an unscheduled visit (i.e. extra day for screening visit if time/schedule did not permit completion over 2 days), or receive a follow-up phone call for evaluation of conditions relating to their participation in the study or the study drug (i.e. ongoing AE that the QI has determined needs to be tracked). The date and reason for these visits/phone calls will be recorded.

### **6.4. PET and MRI scan procedure, data acquisition, and image analysis**

PET measurement of C-raclopride binding to the striatal brain dopamine receptor and C-DTBZ binding to VMAT2 are common, routine procedures used worldwide (e.g., see our publications ref [14, 18] and references therein). Briefly, PET images of C-raclopride (approximately 60 minute) or C-DTBZ (approximately 60 minute) scans will be acquired using CPS-HRRT neuro-PET camera system (Siemens Medical Imaging, Knoxville, TN). Head movement minimization is achieved with a head immobilization system (Tru Scan Imaging, Annapolis USA). Transmission scans will be obtained using a single-photon Cesium ( $E\gamma = 662$  keV) point-source, and used to correct the emission scans for the attenuation of 511 keV photons through tissue and head support.

The PET scans will be initiated following a bolus injection of C-raclopride or C-DTBZ into an arm vein. Raw data are reconstructed by filtered-back projection [19].

MRI (up to approximately one hour): The structural MRI protocol includes the primary structural MRI scan to be used for PET coregistration. This standard spin-echo proton-density weighted protocol (MRI; TE = Min Full, TR = 6000, field of view = 22 cm 2D, slice thickness = 2mm, NEX= 1) will be obtained (Signa 3Tesla GE MRI scanner, (Discovery MR750) General Electric Medical Systems, Milwaukee, WI) for purpose of region of interest (ROI) delineation.

ROI delineation and analysis will be performed following standard operating procedure for PET ROI analysis. In brief, a standard brain template will be transformed to fit individual high-resolution MRI scans, creating ROIs. These will then be refined, aligned and resliced to match the dimension of the PET images. The whole striatum (the primary region of interest) as well as bilateral sub-compartments of the striatum including ventral striatum and pre and post commissural caudate and putamen (as described by Mawlawi [20]) as well as reference tissues (which provide the input function), namely, cerebellar cortex (excluding vermis) for C-raclopride [18] and the occipital cortex for C-DTBZ [21] are selected as ROIs. C-Raclopride and C-DTBZ time activity curves will be obtained from the dynamic data and specific binding (BPND) will be estimated in each ROI. This method has been validated to reliably estimate BPND for C-raclopride (e.g., [22]) and C-DTBZ[14].

We will ensure that scans are not corrupted by motion artefact by de-noising and visually inspecting all images. Should MRI data suggest changes in volume/shape of ROIs, partial volume effect (PVE) adjustment will be made. We will report both PVE corrected and uncorrected data.

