### 3. OBJECTIVE AND HYPOTHESES

Our **Trial Objective** is to establish, in Xyrem®-naïve patients with narcolepsy and in matched controls, whether a single dose of Xyrem® causes changes in striatal binding of C-raclopride and C-DTBZ that would suggest decreased activity of brain dopamine neurones during the initial sedation and increased dopaminergic activity during Xyrem® withdrawal.

Our **WORKING MODEL**, based on our preliminary human PET brain data, is that an initial action of Xyrem® is to cause, during sedation (which is very fast onset with Xyrem®), depressed activity of nigrostriatal dopamine neurones and dopamine release together with marked intraneuronal biosynthesis of dopamine. At this early time, intraneuronal concentrations of dopamine (competing with C-DTBZ at VMAT2) will be high whereas extraneuronal levels of dopamine (competing with C-raclopride at the dopamine receptor) will be low because (we predict) Xyrem® causes accelerated synthesis of dopamine while depressing activity of dopamine neurones.

During drug withdrawal, dopamine that has been building up inside the neurone is released, leading to increased extraneuronal dopamine (accompanied by decreased raclopride binding at the dopamine receptor) and a normalization of dopamine levels inside the neurone. The modestly increased dopamine activity might persist somewhat in drug withdrawal and be beneficial to the patient.

Our **HYPOTHESES**, based on our pilot data and employing a five scan approach, are that, relative to baseline, striatal 1) **C-raclopride binding** will be increased one hour post-Xyrem® but decreased at seven hours, suggesting decreased and increased neuronal dopamine release, respectively, at these times; and 2) **C-DTBZ binding** will be decreased at five hours post-Xyrem®, suggestive of increased intraneuronal vesicular dopamine buildup during Xyrem® exposure. We predict that this biphasic change in dopamine will occur in both narcolepsy and in healthy control study groups.

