The raclopride scan at one hour post- Xyrem® corresponds to the time we found the single dose of Xyrem® to be maximally sedating and for which we anticipate the maximal reduction of dopamine release. Based on our feasibility data, at five hours post-Xyrem®, dopamine should have been "well" accumulated within dopamine neurones and can be assessed by a DTBZ scan. The seven hour C-raclopride scan is conducted during drug withdrawal (approximately 14 Xyrem® half-lives) and would

correspond to the time a subject participates in morning work duties following the typical second night-time Xyrem® dose. This subject therefore might benefit from modest dopamine hyperactivity. Thus, this scan time has been selected for both “clinical” relevance and for logistical considerations.

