### 8.2. Dosage Regimen

Each subject will receive a single oral dose of 3.0 g (6 ml of a 500 mg/ml solution) diluted in 60 ml of water. Subjects will lie down immediately after dosing.

The pilot study 4.5 g dose was selected by [name], Toronto (a consultant who has extensive clinical experience in administration of Xyrem® for narcolepsy; [23-27]) as a commonly used therapeutic dose that is sufficient to cause sedation but can be safely administered to a Xyrem®-naïve subject under supervision. Both [name] and PI believe that sedation will be required for Xyrem® to exert an effect on the dopamine system that can be assessed using C-raclopride or C-DTBZ. Further, it is [name] experience that many subjects receiving smaller doses similar to 2.25 g will not experience somnolence. Regarding safety, we note that in one published Xyrem® multicenter trial in narcolepsy [28] a group of drug-naïve subjects received two 4.5 g doses (spaced 2.5-4 hours apart) *at their homes* (the trial coordinator phoned the subjects after their first night and three times weekly),

and the drug was well-tolerated. In a second study also in narcolepsy patients, the patients received a single initial dose of 4.5 g Xyrem® in a sleep lab setting and the drug was also well-tolerated [29].

The Xyrem® dose we have selected (3.0 g) to carry forward is slightly less than that used in our original study (4.5 g). In the pilot study, using 4.5 g dose of Xyrem® we did encounter subjects who developed nausea, some with vomiting (while lying supine), after ingesting the drug. While listed as a known adverse reaction, this does prevent scanning of the individuals during the earlier time points as they are unable to lie on their back in the scanner. We have chosen to reduce the dose to 3.0 g, which is well within the range of doses used in treatment of narcolepsy as a first dose; and is less likely to induce nausea/vomiting in Xyrem®-naïve subjects than the 4.5 g dose.

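### Beyond head immobilization, the plan names only de-noising and visual inspection against motion; neither corrects head displacement, which could add to or mask the predicted 1-hour raclopride rise

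*Combined protocol and SAP*

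**What the plan says.** Section 6.4 of the protocol has two statements on head motion. At acquisition: "Head movement minimization is achieved with a head immobilization system". In image processing: "We will ensure that scans are not corrupted by motion artefact by de-noising and visually inspecting all images".

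The same section describes dynamic scans of about 60 minutes, attenuation correction from a separate transmission scan, and time-activity curves taken from the dynamic data. One alignment step is described, for regions of interest (ROIs) built from a template fitted to each subject's MRI: "These will then be refined, aligned and resliced to match the dimension of the PET images". ROI analysis is said to follow a standard operating procedure, which is only summarised.

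Section 3 predicts that raclopride binding "will be increased one hour post-Xyrem® but decreased at seven hours". Section 6.1 says the 1-hour scan "corresponds to the time we found the single dose of Xyrem® to be maximally sedating". Section 8.3 expects sedation to last from about 15 minutes to 3.5 hours. Section 7 makes change in binding from baseline the primary endpoint.

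**The concern.** The processing sentence promises an outcome that its two steps cannot deliver. De-noising does not move a displaced head back under the ROI or back into register with the transmission scan. Visual inspection can identify a failed scan but corrects nothing, and it may miss a shift of a few millimetres during part of an hour. The alignment step that is described fits ROIs to the PET images; it does not align PET frames with one another.

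This matters because the endpoint compares scans taken in different states and the expected changes are small. Movement blurs the striatum into low-binding tissue and lowers measured binding, so a difference in movement between two scans appears as a difference in binding. A stiller, sedated 1-hour scan would look higher than baseline, which is the predicted direction. Nausea at that scan would push the other way. The design has no placebo day, and the controls also receive the drug (section 6.1). Comparing groups therefore cannot remove a motion difference that goes with sedation.

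**Working it through.** **1. The plan's own figure.** Section 5.1 states more than 80% power with 15 subjects at alpha 0.05, but prints no SD, so the figure cannot be reproduced. Working backwards with a two-sided paired t-test (n = 15), 80% power needs mean change / SD of change = 0.778. The pilot raclopride means (section 2, two subjects, 4.5 g) are (6 + 13)/2 = +9.5% and (-7 - 6)/2 = -6.5%. The largest SDs of change compatible with 80% power are 9.5/0.778 = 12.2% and 6.5/0.778 = 8.35%.

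**2. State at each raclopride scan.** Baseline: no drug. 1 hour: within the sedated period. 7 hours: after it, since sedation is expected to end by 3.5 hours. Sedation state therefore separates 1 hour from baseline, but not 7 hours from baseline.

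**3. How much binding a displacement can cost.** The documents give no motion data, so this is a toy phantom and every input is an assumption: caudate and putamen as ellipsoids, true binding potential 2.5, Gaussian blur of 3 mm, image shifted along one axis in a share of the frames. Percentage loss in striatal binding:

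| Assumptions | Three axes | Mean |
|---|---|---|
| ROI left at unshifted position, 2 mm, quarter of frames | 4.5 / 0.8 / 1.9 | 2.4 |
| Same, 2 mm, half of frames | 9.0 / 1.6 / 3.7 | 4.8 |
| Same, 3 mm, half of frames | 17.1 / 3.2 / 7.5 | 9.3 |
| Other ellipsoid sizes, ROI unshifted, 2 mm, half | 7.1 / 1.7 / 3.6 | 4.1 |
| Other sizes, ROI at mean head position, 2 mm, half | 4.0 / 0.9 / 2.0 | 2.3 |
| Other sizes, ROI at mean head position, 3 mm, half | 8.6 / 2.0 / 4.3 | 5.0 |

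The mean-position rows are closer to the plan, because section 6.4 aligns ROIs to the PET images. The unshifted rows are upper-end figures.

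**4. From loss to contrast.** Only the difference in motion between scans biases the comparison.

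- Baseline loses L, 1-hour scan still: apparent rise = 1/(1 - L) - 1. L = 2.3% gives 1/0.977 - 1 = 2.4%; L = 4.8% gives 1/0.952 - 1 = 5.0%.
- Baseline still, 1-hour scan loses L, true rise 9.5%: observed = 1.095(1 - L) - 1. L = 2.3% gives +7.0%; L = 4.8% gives +4.2%.

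**5. What it would take to produce both phases from motion alone.** With the 1-hour scan still, a 9.5% rise needs a mean baseline loss of 1 - 1/1.095 = 8.7%. A 6.5% fall at 7 hours then needs a mean loss there of 1 - 0.935/1.095 = 14.6%. Only one entry above exceeds 14.6%: 3 mm, worst axis, half the frames, ROI unshifted.

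**6. Sensitivity of the test.** The chance that a purely artefactual mean shift is declared significant (n = 15, no true effect) comes from the noncentral t on 14 degrees of freedom with noncentrality (shift/SD) x sqrt(15). For 3% and SD 8.35% the noncentrality is 1.39.

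| Assumed SD of change | 2% shift | 3% shift | 5% shift | 3% shift, alpha 0.05/3 |
|---|---|---|---|---|
| 5% | 30% | 58% | 95% | 38% |
| 8.35% | 14% | 25% | 58% | 13% |
| 12% | 9% | 15% | 32% | 6.5% |

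The last column corresponds to Bonferroni adjustment over three pairwise comparisons. The table simplifies section 13: it uses a paired t-test in place of the mixed model and ignores the requirement of a significant time effect first. It shows sensitivity only and does not estimate the actual bias.

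**The case against.** The strongest reply is that silence is not absence. Section 6.4 is written as a summary and cites an operating procedure that the documents do not reproduce; realignment may already be routine at the site, and de-noising may be meant as a step towards it. This stands in part: the text supports saying that no realignment is described, not that none will be done. The sentence as written still names two steps that do not correct displacement.

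Second, immobilization deserves credit. It does, and it makes large average displacements less plausible. It neither measures nor corrects what remains.

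Third, the direction at 1 hour is open. Section 8.2 reports nausea and vomiting in the pilot and says "this does prevent scanning of the individuals during the earlier time points as they are unable to lie on their back in the scanner". That line concerns the 4.5 g pilot and scans that could not be done, so it is evidence about missing scans rather than moving ones. The 3.0 g dose was chosen partly to make nausea less likely. This stands: the bias could go either way.

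A reader might go further and infer that motion could produce the whole predicted pattern, a rise and then a fall. The documents do not support that. Sedation state does not separate 7 hours from baseline, and the required losses are reached only at the phantom's extreme. Restlessness late in a visit of about 10 hours is conceivable, but no motion data bear on it, and the baseline visit is itself about seven hours with an MRI and two PET scans.

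**Conclusion.** The point holds in a limited form. Apart from immobilization, the plan describes nothing that corrects, measures or compares head motion, although its primary endpoint is a within-subject change of roughly 6 to 13% between scans in different states. Less motion under sedation could contribute to the 1-hour rise; motion from nausea could hide it.

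The size and direction of any bias are unknown. If the 1-hour scan were perfectly still and the baseline head displaced by 2 mm in half its frames, the apparent rise would be about 2.4 to 5.0% averaged over directions. This is an upper-end illustration resting on assumed anatomy, resolution and motion. A shift of that order would raise the chance of a false positive well above 5% if the SD of change is small, and less so if it is near 12%. The point does not extend to explaining the 7-hour fall and does not show that the pilot findings were artefact. It justifies a change of method, since a better and cheap one is available.

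**What to change.** Replace the motion sentence in section 6.4 with:

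> All dynamic scans will be corrected by frame-to-frame realignment to a common reference frame, with a check of alignment to the transmission scan, before time-activity curves are extracted; images will then be visually inspected blind to time point. Mean displacement per scan will be tabulated by time point and group, and a sensitivity analysis will omit scans with large residual displacement, using a limit fixed before analysis.

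The limit is for the investigators to set; the documents give no motion data from which to derive one. It belongs in a sensitivity analysis and not in a primary exclusion rule, because groups of at most 15 cannot readily lose scans. Realignment does not correct motion within a frame, so inspection stays as a final check.

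The cost is a few hours of processing per subject on data already being acquired, with no additional scans, radiation or visits. If the operating procedure already includes realignment, the cost of that part is one sentence saying so.

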## 7. EFFICACY VARIABLES AND ANALYSIS

The **primary endpoint** is the change in C-raclopride or C-DTBZ BP in whole striatum, caudate, putamen, and bilateral sub-compartments of the striatum, from baseline scan vs. that at one, 5 and 7 hour scans.

The **secondary endpoint** is the blood concentration of GHB (expressed as the area under the curve; AUC) at 0.5, 1, 3, 5 and 7 hours following ingestion of GHB.

## 8. STUDY DRUG

### 8.1. Drug Formulation

Each bottle contains 180 ml of Xyrem® at a concentration of 500 mg/ml. Xyrem® is supplied as a kit, containing a press-in-bottle adapter and a 10 ml oral measuring device (plastic syringe). The pharmacy will provide a 100 ml dosing bottle.

### 8.2. Dosage Regimen

Each subject will receive a single oral dose of 3.0 g (6 ml of a 500 mg/ml solution) diluted in 60 ml of water. Subjects will lie down immediately after dosing.

The pilot study 4.5 g dose was selected by [name], Toronto (a consultant who has extensive clinical experience in administration of Xyrem® for narcolepsy; [23-27]) as a commonly used therapeutic dose that is sufficient to cause sedation but can be safely administered to a Xyrem®-naïve subject under supervision. Both [name] and PI believe that sedation will be required for Xyrem® to exert an effect on the dopamine system that can be assessed using C-raclopride or C-DTBZ. Further, it is [name] experience that many subjects receiving smaller doses similar to 2.25 g will not experience somnolence. Regarding safety, we note that in one published Xyrem® multicenter trial in narcolepsy [28] a group of drug-naïve subjects received two 4.5 g doses (spaced 2.5-4 hours apart) *at their homes* (the trial coordinator phoned the subjects after their first night and three times weekly),

and the drug was well-tolerated. In a second study also in narcolepsy patients, the patients received a single initial dose of 4.5 g Xyrem® in a sleep lab setting and the drug was also well-tolerated [29].

The Xyrem® dose we have selected (3.0 g) to carry forward is slightly less than that used in our original study (4.5 g). In the pilot study, using 4.5 g dose of Xyrem® we did encounter subjects who developed nausea, some with vomiting (while lying supine), after ingesting the drug. While listed as a known adverse reaction, this does prevent scanning of the individuals during the earlier time points as they are unable to lie on their back in the scanner. We have chosen to reduce the dose to 3.0 g, which is well within the range of doses used in treatment of narcolepsy as a first dose; and is less likely to induce nausea/vomiting in Xyrem®-naïve subjects than the 4.5 g dose.

### **8.3. Washout Period**

Xyrem® is rapidly eliminated by metabolism with a plasma half-life of approximately 0.5 to 1 hour and time to peak plasma concentration of 0.5 to 1.25 hours (Xyrem® monograph).

The almost certain (>95%) consequence of a single 3.0 g dose of Xyrem® is reversible sedation, depressed consciousness, and possibly sleep lasting approximately 15 minutes to 3.5 hours. Vital signs (HR, BP, respiration rate, oxygen saturation) and level of consciousness will be regularly monitored immediately before (baseline measurement) and post-Xyrem® by an anesthesiologist, working under supervision of [name], the QI. The anesthesiologist present for the Xyrem® dose will also establish and sign-off (with co-sign-off by RC or PI) when the subject can safely leave (by taxi or driven by companion) the PET Centre (estimated 6 hours post drug). Subject will be contacted by phone the following morning, by RC and/or PI for a brief interview to enquire about their wellbeing since leaving the PET Centre.

## **9. CONCOMITANT MEDICATION**

Subjects will be carefully screened at the beginning of the study to ensure that they are healthy and safely able to take Xyrem®. If subjects are currently on medication (including antidepressants for cataplexy) to treat a medical or mental illness, this condition must be stable/controlled, and they must be on a stable dose of said medication. The QI will determine whether the subjects' medications would be contraindicated. On the Xyrem® Scan day, specifically disallowed drugs/medications are any sedative-hypnotics, or any other CNS depressants including alcohol.

## **10. RESCUE MEDICATION AND RISK MANAGEMENT**

### **10.1. Risks from Xyrem®**

Our primary goal is the prevention of the two main predictable possible adverse events (airway obstruction and/or central respiratory depression from oversedation, aspiration of gastric contents). To this end we first undertake to review carefully the reports of the candidates' history and physical examinations before they enter the study to try to identify co-morbidities that might put the subjects at increased risk. If needed, a joint discussion with the QI, [name] and the PI would ensue to resolve issues identified before enrollment would continue.

While sedation is anticipated, significant respiratory depression with the dose proposed is not. If present, the drug profile indicates that this would be self limiting (i.e. does not require an antidote) and of short duration (2-3 hours). In this regard, data from a recent investigation of GHB overdose cases suggest that most such subjects coming to the ER do not actually require intubation and are managed conservatively by lateral positioning, either oropharyngeal or nasopharyngeal airway adjuncts, and close physiological and neurological monitoring [30].

During the study when Xyrem® is administered the anesthesiologist will monitor the subject's level of consciousness and vital signs. The physiological monitor in this unit will allow continuous display of oxygen saturation, HR, respiratory rate and intermittent blood pressures. Based on [name] experience with Xyrem®, we expect that no subject will require any intervention, including oxygen. However a variety of ancillary airway devices will be available including the ability to give oxygen by nasal prongs and mask, address airway obstruction (oral and nasal airways, laryngeal masks), manually ventilate (Laerdal bag and mask), intubate (suction, laryngoscope, endotracheal tubes), medications for sedation (midazolam, propofol), muscle relaxation (succinylcholine, rocuronium), inotropic support and emergency management (ephedrine, epinephrine, phenylephrine). While we do not expect that interventions other than simple airway management will be needed, the anesthesiologist will have the expertise, skill set and equipment to protect the airway and manage ventilation if called upon. The spectrum of interventions that will be available is large and will be dictated by the patient's condition.

Per CAMH policy, a code blue call to Switchboard must be made, for example, in cases of respiratory arrest or significant depression of respiration or aspiration of vomit causing choking. Again, the anesthesiologist has the expertise to manage these issues. In these scenarios Switchboard would not be instructed to call 911 at the time of the code blue call as the resources within the unit are expected to meet the clinical needs. However, the CAMH-College Street site Attending Physician/Duty Doctor/Medical Doctor, who proceeds to the scene, leads the code and will determine whether a 911 call needs to be made. An external 911 call will be made if the subject does not respond to the management provided by the anesthesiologist or is considered by either the anesthesiologist or attending medical staff to require outside intervention because of a critical condition. An example would be signs of cardiac arrest or instability. In the unlikely event that it was felt that a transfer to an emergency department was indicated this would be activated according to the priority of the clinical situation. The anesthesiologist would accompany the patient to the ER.

Based on measurement of vital signs (HR, BP, respiration rate, oxygen saturation) and level of consciousness, the anesthesiologist will establish and sign-off (with co-sign-off by RC or PI) when the subject can safely leave (by taxi) the PET Centre (estimated 6 hours post drug). Subject will be given a wallet card printed with study details (e.g., Xyrem® dose, date and time taken, precautions/warnings, contact information for study personnel) and told that this should be kept on them (in their wallet) as a reminder of the precautions necessary and also as emergency contact information. Subject will be contacted by phone by PI and/or RC the following morning to enquire about his/her wellbeing since leaving the PET Centre.

There are other risks associated with Xyrem® (estimated from clinical trial data employing a variety of doses taken chronically) including headache, unspecified pain, confusion, diarrhea, urinary incontinence, and insomnia. As GHB can be an abused drug, there is generic (we feel very low) risk that the subjects might "like" the GHB experience and wish to take the drug recreationally. This risk is minimized by selecting subjects who do not have a history of substance abuse.

